## Usage of Facebook

The research study would like to incorporate the usage of Facebook in the study. We plan on using Facebook in the following ways.

## 1) Recruitment

- a. The study has created digital ads (submitted with this amendment) that will be used in Facebook ads. Ads posted will be pop up ads.
- 2) Study Notifications & Contact Method
  - a. The study will set up a Facebook page in which participants will be given the link (usage will not be required but will be an additional method that participants can

use to contact study staff or find out study information). A description of this usage is listed below.

- i. Study info such as press releases, news articles, manuscripts will be posted to the study Facebook page. This information will also be provided in study newsletters (for those not on Facebook).
- ii. Information regarding site closings (such as in the event of inclement weather or holidays) or intervention materials (group intervention classes) will be posted on the Facebook page. Please note all participants will be given information regarding holiday closings and weather policies in their intervention classes. A study phone number will be given to each participant which will be updated in the event of a closing. It will not be necessary to check Facebook to learn of a study closing.
- iii. Participants in the study will also be able to use Facebook as a means of contacting the staff by sending a private message (email) to the staff. This method may be useful to the nutrition and health group in which participants will be given a choice to their preferred method of contact (email, phone, Facebook private message).
- 3) Participant Posting
  - a. The study will set up its account as a page therefore it will not be a private group. Therefore the study will only post study information (press releases, articles, etc.) and site information. We will not post pictures or study participant information. However participants whom are on Facebook will be allowed to post to the study page. All posts will be reviewed by the study staff to ensure no other participants are identified as being a part of the study.

# **Informed Consent**

Signed informed consent will be obtained from each subject. Consent will be obtained by study coordinator, interventionists, and testing staff. Participants will be consented at screening visit one (SV1). Upon arrival each potential subject will meet with a staff member to review the study consent form. No study specific procedures will be done prior to the signing of the consent form. Staff members administering the informed consent must use the following steps in order to orient the potential subject to the purpose of the research.

- The staff member will verbally explain the study to the potential subject, providing all pertinent information (purpose, procedures, risks, etc.), and will allow the potential subject ample opportunity to ask questions.
- Following this verbal explanation, the potential subject will be provided with the consent form and schedule to review. The potential subject will be given as much time as they need to consider whether or not to participate in the research.
- After allowing time for the potential subject to read the consent form, the staff member, will meet with the potential subject to answer any additional questions he/she may have.

- Once the potential subject has all of their questions answered and has agreed to participate, they will be asked to sign and date the consent form. The staff member will also sign and date the consent.
- A copy of the informed consent will be made and given to the subject.

In the event a person wishes to discuss the study with a family member or would like additional time to think about participating in the study, the staff member will make a note of this in the subject file and the staff will follow-up with the potential subject.

Once a person has completed the screening appointment and the data has been entered into study website the project manager will randomize the subject by selecting the randomization program in the WE-CAN website. Participants will be placed into either the diet & exercise group or the attention control (nutrition & health) group.

# **Safety Monitoring Plan**

An internal safety committee has been established to monitor participant safety and to evaluate the progress of the study. In addition NIAMS has selected a DSMB to monitor study safety and progress.

# Adverse Event and Serious Adverse Event Collection and Reporting

Adverse Event (AE) - An AE is any unfavorable and unintended diagnosis, sign (including an abnormal laboratory finding), symptom, or disease temporarily associated with the study intervention, which may or may not be related to the intervention, including excessive delayed onset muscle soreness (DOMS) as some minimal muscle soreness will be expected after the training session. AEs include any new events not present during the pre-intervention period or events that were present during the pre-intervention period which has increased in severity. Participants will be asked if any events have occurred on a monthly basis prior to their intervention class and at each testing session. Participants will be encouraged to report AEs as they occur.

Study staff will report non-serious adverse events (related and unrelated to the study) to site project manager and principal investigator within 7 days of notification of the event and will be reported to the coordinating center quarterly. Testing staff will inquire about adverse events prior to testing to ensure there are no unreported events. The site physician/PA will review non serious adverse events (AE) on a weekly basis. Non serious adverse events will be included in the NIAMS safety report and submitted biannually.

Serious Adverse Event (SAE) - An SAE is any untoward medical occurrence that results in death, is life-threatening, requires or prolongs hospitalization, causes persistent or significant disability/incapacity, results in congenital anomalies/birth defects, or, in the opinion of the investigators, represents other significant hazards or potentially serious harm to research participants or others.

Staff will report serious adverse events (related and unrelated to the intervention) to the site project manager, principal investigator, and study physician. The clinical site will reports SAEs

to the coordinating center within 24 hrs of notification. SAEs will be reported to NIAMS within 24 hours of being reported to the PI (within 48 hours of initial report). The WFU IRB does not require the reporting of adverse events unless it is serious, unexpected and related to the study. Follow-up information will be provided to the PI, DSMB/Safety Officer, and IRB, as appropriate.

NIAMS has assigned a Data Safety Monitoring Board (DSMB) or safety monitor to monitor all aspects of the study.

The DSMB/Safety Monitor will have the following charges:

• To review the entire study protocol, the operations manual, and the informed consent and assent forms for recruitment, randomization, intervention, participant safety, data management, auditing plans for participant records, and quality control and analysis plans, and to identify needed modifications.

• To review data related to efficacy, recruitment, randomization, compliance, retention, protocol adherence, trial operating procedures, forms completion, intervention effects, gender and minority inclusion, and participant safety over the course of the trial.

• To identify problems related to safety over the course of the study and to report them in writing to the PIs, who will ensure that the appropriate individuals receive the report.

• To identify a need for additional data relevant to safety and to request them from investigators.

• To propose appropriate analyses and periodically review developing data on safety and endpoints.

• To make recommendations regarding recruitment, intervention effects, retention, compliance, safety, and continuation of the study.

• To send the Program Administrator and PIs written reports following each DSMB meeting, addressing all issues raised, and subsequently sent to the IRB.

• At any time, the DSMB may recommend discontinuation of any component/intervention of the study for any of the following reasons:

1) Compelling evidence from this or any other study of an adverse effect sufficient to override any potential benefit of the interventions to the target population.

2) Compelling evidence from this or any other study of a significant beneficial effect whose continued denial to other study group(s) would be unethical.

3) A very low probability of addressing the study hypothesis within a feasible time frame.

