## Study Design

We will randomize 820 overweight and obese (BMI  $27 \ge kg/m^2$ ), adults age  $\ge 50$  yrs knee OA into one of 2 groups: an intensive dietary restriction-plus-exercise (D+E) group or an attention control (nutrition and health) group. Persons who have begun screening once we hit our overall recruitment goal of 820 will be allowed to complete the screening process therefore up to 840 persons may be enrolled into the study. Forsyth, Johnston, and Haywood Counties' recruitment goals are 420, 210, and 210, (total 840) respectively. Our minimum weight-loss goal for the weight-loss group will be 10% of body weight. The exercise intervention will meet 3 days/wk at the clinical site. The intervention will be comprised of both aerobic and strength training exercises. When participants are unable to come into the facility for intervention, sessions will be conducted via phone or through video conferencing. The nutrition and health group will meet 5 times over an 18 month period and receive a combination of webinars, video messages, text messages, emails (via personal email or Facebook), phone calls, and mailings for the remaining months. Participants will be allowed to choose their preferred method.

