### Months 13-18

Period 3 will emphasize weight management over time, with 1 monthly individual contact. Weight loss can continue throughout the intervention, provided the participant wants to and has not reached a level associated with health hazards; i.e. a 20% body weight loss at 6 months or >30% at 12 months. Participants will continue to follow a

weekly menu plan with recipes using traditional foods and the option to incorporate meal replacements.

The exercise intervention will cover an 18-month period. The exercise program will consist of a 15-minute aerobic phase, a 20-minute strength-training phase, a second 15-minute aerobic phase, and a 10-minute cool-down phase. These sixty-minute exercise sessions will be conducted three days per week (two days/week will be center based). Each participant will be prescribed an individual walking prescription by the exercise leader, which will be adjusted accordingly, as each participant progresses throughout the 18 months. The exercise will be of moderate intensity. Alternate forms of aerobic exercise, such as but not limited to stationary bike, elliptical trainer, or treadmill walking, can be used in place of over-ground walking. This choice could be based on participant preference, the limitations of the exercise facility, or the participant's pain level. To motivate participants to be physically active intervention staff will plan an optional fun walk. The walk will take place at Wake Forest University. Participants do not have to participate in the walk in order to be in the study. If a participant chooses to participate in the walk they will be asked to sign a waiver.

Intervention Locations: *Forsyth County:* The diet and exercise classes will be offered at a number of sites within Winston-Salem. Participants will be allowed to pick the location that is most convenient for them to attend. Classes will take place at the Clinical Research Center on the Wake Forest University Campus, at St. Peter's World Outreach Center, and at Smiley's Fitness. *Haywood County:* The diet and exercise classes will be held at the Haywood Regional Health & Fitness Center in Waynesville, NC. *Johnston County:* The diet and exercise classes will be held at the Clayton Community Center and the Johnston Medical Mall. Participants will also be allowed to exercise outdoors at the intervention sites when the weather permits. Staff will schedule set times when outdoor walking will be allowed.

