The following measures will be taken in the event participants are unable to come into the facility:

- Virtual Sessions Participants will be given the option to attend virtual exercise and diet classes. Intervention classes will be taught via Zoom. Participants will be provided with the class login information. The group and diet exercise sessions will be recorded and posted to our study Facebook page as well as sent to participants who are unable to attend the live sessions. Recordings will be edited so that only the class exercise and diet instruction can be viewed (beginning and end of the session as participants log in and out will be cut out of the video). As a security measure the virtual classes will be locked after 10 minutes so that no others can join the class. Additionally participants will not be given access to record the session. Individual sessions will also be conducted via Zoom.
- 2. Phone Sessions Staff will call participants to deliver the diet group and individual session content. All participants have previously been provided with at home exercise manuals. Staff will also use this time to review our non-facility-based exercise plans.

3. Email Sessions – Participants may also choose to receive the diet group and individual session content via email. All participants have previously been provided with at home exercise manuals. Staff will also use this time to review our non-facility-based exercise plans.

All intervention staff in the WE-CAN study will be CPR certified. The exercise coordinator, who is part of the coordinating center and is responsible for maintaining exercise protocol congruity between the intervention sites, will train and supervise the intervention staff. Intervention staff will meet monthly with the exercise coordinator to discuss any potential problems, risks, and concerns that have risen. AEDs will be available at each location. Emergency drills will be performed monthly in addition the AED will be checked monthly. The clinical research center (Forsyth), Johnston Medical Mall (Johnston), and the Haywood Regional Health and Fitness Center (Haywood) also house cardiac rehabilitation programs and will also have crash carts available.

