## Nutrition & Health Intervention

The nutrition and health (attention control) intervention will cover an 18-month period. There will be five total face to face group meetings over the 18 months, with one meeting each at months 1, 3, 6, 9, and 15; and during the other months (months 2, 4-5, 7-8, 10-14, 16-18) participants will receive a combination of informational packets, webinars, text messages, and emails. Participants will be able to select their preferred method. Each group meeting will last approximately one hour and will be held at St. Peter's World Outreach Center and at Senior Services in Winston-Salem, NC. The sessions will be interactive and will provide useful information on such topics as proper foot care, general nutrition, health behaviors, management of medications, and sleep practices. The Community Advisory Board will give input on the class sessions.

Experts across a broad range of relevant topics that are of interest to older adults will provide information via information packets, webinars, text messages or emails. These monthly contacts and email blasts will keep the participants in the nutrition and health group engaged in the WE-CAN study and will increase adherence to the group sessions and the testing visits.

Participants in both interventions will be provided with items with the study logo such as t-shirts and tote bags to promote group bonding and study adherence. Additionally, giftcards will be raffled at various class sessions. In order to better balance the amount of money spent on the two groups participants in the Nutrition & Health group will receive a \$100 (gift cards) for completing the testing appointments. They will be given \$25 at 6 months and \$75 at 18 months. At the 12-month testing appointments the participants will receive an incentive with the study logo. Participants in the Diet & Exercise group will be receiving meal replacements for the first year of the study.

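### The monthly adverse-event question is tied to a class that controls attend in only 5 of 18 months, leaving 11 control months with no stated way of being asked

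*Combined protocol and SAP*

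**What the plan says.** The rule for asking is in Adverse Event and Serious Adverse Event Collection and Reporting: "Participants will be asked if any events have occurred on a monthly basis prior to their intervention class and at each testing session". The same section encourages participants to report events themselves. It has testing staff check for unreported events before testing, and a site physician or PA reviews non-serious events weekly. The event definition extends to training effects, "including excessive delayed onset muscle soreness (DOMS) as some minimal muscle soreness will be expected after the training session". On reporting: "Non serious adverse events will be included in the NIAMS safety report and submitted biannually". The DSMB's listed charges include reviewing accumulating safety data.

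The class schedules differ by arm. For D+E, the exercise description under Months 13-18 covers the full 18 months: "These sixty-minute exercise sessions will be conducted three days per week (two days/week will be center based". When participants cannot attend, sessions may be virtual, recorded, by phone or by email: "Participants may also choose to receive the diet group and individual session content via email". No adverse-event question is attached to those alternatives.

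For controls, Nutrition & Health Intervention gives "five total face to face group meetings over the 18 months, with one meeting each at months 1, 3, 6, 9, and 15", with remote material in the other months. Its stated purpose is engagement and adherence: "These monthly contacts and email blasts will keep the participants in the nutrition and health group engaged in the WE-CAN study". Study Design adds "phone calls, and mailings for the remaining months". Neither section attaches an adverse-event question to these contacts.

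The table in Procedures-Screening and Follow-up Visits places Adverse Events among the questionnaires at FU6, FU12 and FU18, and as they occur. The text below it gives a reduced questionnaire list for remote testing. That list is stated to be exclusive and names neither adverse events nor medical history.

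**The concern.** A rule that sounds identical for the two arms hangs on an event, the intervention class, that is far more frequent in one of them. Minor events are sensitive to how often people are asked about them. If D+E participants are asked every month and controls about every third month, a by-arm listing of non-serious events can show more in D+E partly because of the asking. That would add to any genuine excess, such as the muscle soreness named in the definition. What is at stake is how the safety reports are read, since the DSMB may recommend discontinuing a component for adverse effects. An event never asked about and never volunteered cannot be restored at analysis, so the remedy belongs at collection.

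**Working it through.** **Inputs**
- Control meeting months, M = {1, 3, 6, 9, 15} (Nutrition & Health Intervention).
- Control months without a meeting: 2, 4, 5, 7, 8, 10 to 14 and 16 to 18 (same section).
- Testing months in both arms, T = {6, 12, 18} (Procedures-Screening and Follow-up Visits).
- D+E class months: 1 to 18, from several exercise sessions a week over 18 months (Months 13-18).

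**The plan's own figure.** M has 5 months, matching the five meetings in Study Design. The non-meeting list has 13. 5 + 13 = 18 with no overlap, so the control calendar is complete and consistent.

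**Reading 1: asking follows classes and visits.**
- Control: M ∪ T = {1, 3, 6, 9, 12, 15, 18}. The count is 5 + 3 − 1 = 7, because month 6 has both a meeting and a visit.
- Months without a question: 18 − 7 = 11, namely {2, 4, 5, 7, 8, 10, 11, 13, 14, 16, 17}.
- Intervals from month 0 to each successive question: 1, 2, 3, 3, 3, 3, 3 months. They sum to 18, and the longest is 3.
- D+E: up to 18 of 18. This is a ceiling, because it assumes attendance at a session where the question is put.

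**Reading 2: a monthly question is meant for both arms.** Controls then need 18 monthly questions. In 13 months there is no class to precede. Testing visits cover two of those (months 12 and 18), so 13 − 2 = 11 months have no described route. Both readings leave the same 11 months to resolve.

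**Remote testing, sections side by side.** The adverse event section requires the question at every testing session. The visit table classes Adverse Events as a questionnaire. The remote list says only the named questionnaires are collected, and Adverse Events is not among them. These three statements need reconciling, in both arms.

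**What the count does not give.** It measures occasions for asking, not events captured. The documents state no capture rate with or without a prompt and no attendance figure, so no ratio of reported events can be derived.

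**The case against.** The strongest reply is that the sentence says monthly and makes no exception for controls. They receive some contact in every month, including phone calls according to Study Design, so a monthly question is feasible and its route may be in the operations manual that the DSMB charges mention. That stands as far as it goes: a reader might infer that the protocol intends controls to be asked only seven times, and the text does not establish this. It also does not say how else they are asked, and the class it names does not exist in 13 control months.

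The second reply is that less frequent asking mostly delays capture. Before testing, staff look for unreported events. At in-person visits, Medical History FU at FU6, FU12 and FU18 is meant partly to record changes in health, and the Comorbidities Questionnaire is repeated at FU12 and FU18. Participants are encouraged to report events as they happen. On the schedule, an event is missed only if it is neither volunteered nor recalled at a question at most 3 months later. This stands and limits the size of the problem, though minor transient events are the kind most easily forgotten.

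Third, it is tempting to say that a real D+E excess and one produced by asking would be inseparable. That goes too far: event type, for example excessive soreness after training, and physician/PA review help to distinguish them.

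Fourth, a reader might infer from the reduced remote list that the question is dropped at testing visits altogether. That would require every visit to be remote and the rule for every testing session to be ignored. The wording is ambiguous and needs reconciling; it is not evidence of such a gap.

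**Conclusion.** The point holds in a limited form. As written, the monthly rule cannot be carried out in the control arm. Followed through classes and visits, it gives 7 of 18 months in control against up to 18 of 18 in D+E. Read as monthly for all, it leaves 11 control months without a stated route in the protocol or SAP.

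The consequence is confined to any by-arm summary of non-serious events in the NIAMS or DSMB reports. The documents describe no such table and no between-arm test of adverse events, and adverse events are not an endpoint, so no planned efficacy inference is affected. The likely direction is to overstate harm in D+E; nothing here suggests that harm is hidden. The size is unknown. Serious events should be less affected: resource use, including clinician visits and surgery, is collected in both arms at all three follow-up visits and, as a cost-effectiveness questionnaire, remains on the remote list.

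The conclusion assumes that the operations manual does not already settle the matter. It is worth correcting because the data go to the bodies overseeing safety and the correction is cheap.

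**What to change.** In the adverse event section, set one monthly adverse-event question for both arms, independent of class attendance. For controls in months with neither a meeting nor a testing visit, attach it, with a reply requested, to the monthly contact they already receive under Study Design and Nutrition & Health Intervention. Attach the same question to the D+E virtual, phone and email sessions. In Procedures-Screening and Follow-up Visits, state that the adverse-event inquiry is kept at remote testing sessions, so that the reduced list agrees with the visit table and the adverse event section. If the operations manual already provides all this, a sentence saying so is enough.

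The cost is protocol wording and staff time for handling replies and chasing non-responders. The ceiling is 11 replies per control participant: 410 × 11 = 4,510 over the trial, or 420 × 11 = 4,620 if enrollment reaches the permitted 840, plus replies from D+E remote sessions. A remote reply is not fully equivalent to being asked in person, so the imbalance is reduced rather than removed.
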